#### **7.1.3 Methods for Evaluation of Measurable Disease**

All measurements will be taken and recorded in metric notation using a ruler or calipers. All baseline evaluations will be performed as closely as possible to the beginning of treatment and never more than 30 days before the beginning of the treatment.

The same method of assessment and the same technique will be used to characterize each identified and reported lesion at baseline and during follow-up whenever feasible. Imaging-based evaluation is preferred to evaluation by clinical examination when both methods have been used to assess the antitumor effect of a treatment.

**Clinical lesions:** Clinical lesions will only be considered measurable when they are superficial (e.g., skin nodules and palpable lymph nodes) and  $\geq 10$  mm ( $\geq 1$  cm) diameter as assessed using calipers (e.g., skin nodules). In the case of skin lesions, documentation by color photography, including a ruler to estimate the size of the lesion, is recommended.

**Chest x-ray:** Lesions on chest x-ray are acceptable as measurable lesions when they are clearly defined and surrounded by aerated lung. However, CT is preferable.

**Conventional CT and MRI:** This guideline has defined measurability of lesions on CT scan based on the assumption that CT slice thickness is 5 mm (0.5 cm) or less. If CT scans have slice thickness greater than 5 mm (0.5 cm), the minimum size for a measurable lesion should be twice the slice thickness. MRI is also acceptable in certain situations (e.g. for body scans).

Use of MRI remains a complex issue. MRI has excellent contrast, spatial, and temporal resolution; however, there are many image acquisition variables involved in MRI, which greatly impact image quality, lesion conspicuity, and measurement. Furthermore, the availability of MRI is variable globally. As with CT, if an MRI is performed, the technical specifications of the scanning sequences used should be optimized for the evaluation of the type and site of disease. Furthermore, as with CT, the modality used at follow-up should be the same as was used at baseline and the lesions should be measured/assessed on the same pulse sequence. It is beyond the scope of the RECIST guidelines to prescribe specific MRI pulse sequence parameters for all scanners, body parts, and diseases. Ideally, the same type of scanner should be used, and the image acquisition protocol should be followed as closely as possible to prior scans. Body scans should be performed with breath-hold scanning techniques, if possible.

**PET-CT:** At present, the low dose or attenuation correction CT portion of a combined PET-CT is not always of optimal diagnostic CT quality for use with RECIST measurements. However, if the site can document that the CT performed as part of a PET-CT is of identical diagnostic

quality to a diagnostic CT (with IV and oral contrast), then the CT portion of the PET-CT can be used for RECIST measurements and can be used interchangeably with conventional CT in accurately measuring cancer lesions over time. Note, however, that the PET portion of the CT introduces additional data which may bias an investigator if it is not routinely or serially performed.

**Tumor markers:** Serum PSA will be used as part of the composite response definition as outlined in Section 2 and Section 8 of the protocol.

#### 7.1.4 Response Criteria

##### Evaluation of Target Lesions

###### Complete Response (CR)

Disappearance of all target lesions, determined by two separate observations conducted not less than 4 weeks apart. Any pathological lymph nodes (whether target or non-target) must have reduction in short axis to <10 mm (the sum may not be "0" if there are target nodes). There can be no appearance of new lesions.

###### Partial Response (PR)

At least a 30% decrease in the sum of the longest diameter (LD) of target lesions, taking as reference the baseline sum LD. There can be no appearance of new lesions.

###### Progressive Disease (PD)

At least a 20% increase in the sum of the diameters of target lesions, taking as reference the smallest sum on study (this includes the baseline sum if that is the smallest on study). In addition to the relative increase of 20%, the sum must also demonstrate an absolute increase of at least 5 mm (0.5 cm). (Note: the appearance of one or more new lesions is also considered progressions).

###### Stable Disease (SD)

Neither sufficient shrinkage to qualify for PR nor sufficient increase to qualify for PD, taking as reference the smallest sum LD since the treatment started.

##### Evaluation of Non-Target Lesions

###### Complete Response (CR)

Disappearance of all non-target lesions and normalization of tumor marker level. All lymph nodes must be non-pathological in size (< 10 mm short axis).

Note: If tumor markers are initially above the upper normal limit, they must normalize for a patient to be considered in complete clinical response.

###### Incomplete Response/Stable Disease (SD)

Persistence of one or more non-target lesion(s) and/or maintenance of tumor marker level above the normal limits.

###### Progressive Disease (PD)

Appearance of one or more new lesions and/or unequivocal progression of existing non-target lesions.

## **Evaluation of Best Overall Response**

The best overall response is the best response recorded from the start of the treatment until disease progression/recurrence (taking as reference for progressive disease the smallest measurements recorded since the treatment started). The participant's best response assignment will depend on the achievement of both measurement and confirmation criteria.

**Table 7.1 Response Criteria For Participants with Measurable Disease (i.e., Target Disease)**

Target Lesions	Non-Target Lesions	New Lesions	Overall Response	Best Overall Response when Confirmation is Required*
CR	CR	No	CR	≥4 wks. Confirmation**
CR	Non-CR/Non-PD	No	PR	≥4 wks. Confirmation**
CR	Not evaluated	No	PR	
PR	Non-CR/Non-PD/not evaluated	No	PR	
SD	Non-CR/Non-PD/not evaluated	No	SD	Documented at least once ≥4 wks. from baseline**
PD	Any	Yes or No	PD	no prior SD, PR or CR
Any	PD***	Yes or No	PD	
Any	Any	Yes	PD	

\* See RECIST 1.1 manuscript for further details on what is evidence of a new lesion.

\*\* Only for non-randomized trials with response as primary endpoint.

\*\*\* In exceptional circumstances, unequivocal progression in non-target lesions may be accepted as PD.

Note: Participants with a global deterioration of health status requiring discontinuation of treatment without objective evidence of PD at that time should be reported as "*symptomatic deterioration*." Every effort should be made to document the objective progression even after discontinuation of treatment.

**Table 7.2 Response Criteria for Participants with Non-Measurable Disease (i.e., Non-Target Disease)**

Non-Target Lesions	New Lesions	Overall Response
CR	No	CR
Non-CR/non-PD	No	Non-CR/non-PD*
Not all evaluated	No	not evaluated
Unequivocal PD	Yes or No	PD
Any	Yes	PD

\* 'Non-CR/non-PD' is preferred over 'stable disease' for non-target disease since SD is increasingly used as an endpoint for assessment of efficacy in some trials so to assign this category when no lesions can be measured is not advised

## **Duration of Response**

### Duration of overall response

The duration of overall response is measured from the time measurement criteria are met for CR or PR (whichever is first recorded) until the first date that recurrent or progressive disease is objectively documented (taking as reference for progressive disease the smallest measurements recorded since the treatment started).

The duration of overall CR is measured from the time measurement criteria are first met for CR until the first date that recurrent disease is objectively documented.

#### Duration of stable disease

Stable disease is measured from the start of the treatment until the criteria for progression are met, taking as reference the smallest measurements recorded since the treatment started.

#### Progression-Free Survival

Progression-free survival (PFS) is defined as the duration of time from start of treatment to time of progression or death, whichever occurs first.

#### Evaluation of non-measurable bone disease per PCWG3 criteria

Bone scans obtained after the baseline evaluation will be used to evaluate post-treatment changes. Bone scans obtained will be evaluated as either “no new lesions” or “new lesions” on the tumor measurement forms.

- For the first scheduled reassessment: If 2 or more new bone lesions are detected at the first scheduled evaluation (9 weeks), confirmatory bone scan is required 6 or more weeks later. If  $< 2$  additional new lesions are observed on the confirmatory bone scan, study therapy is continued. If  $\geq 2$  additional new lesions are observed, then the patient has experienced radiographic progression by PCWG criteria. Progression in this situation is dated as the time of the first reassessment scan.
- For subsequent scheduled reassessments: If no new lesions are observed, study therapy will continue. If  $\geq 2$  new bone lesions are observed, this is evidence of radiographic PD. Date of progression is the date at which the first scan demonstrating radiographic progression was obtained.

#### Evaluation of Post-treatment PSA changes

All patients will be evaluated for PSA decline. Patients with disease that is not measurable will be eligible for this study and will be assessed for response based on changes in PSA and serial bone scans (if appropriate). The baseline serum PSA must be at least 2 ng/mL to be evaluable for PSA response.

- 50% and 90% PSA Decline: PSA decline of at least 50% and 90%, respectively, from baseline confirmed by a second measurement at least 3 weeks later. The reference for these declines should be a PSA measured within 2 weeks prior to starting therapy.
- PSA Progression: Prostate Cancer Working Group 3 (PCWG3) Criteria will be reported. PSA progression occurs when the PSA has increased 25% or greater above nadir and an absolute increase of 2 ng/mL or more from the nadir is documented. Where no decline is observed, PSA progression similarly occurs when a 25% increase from baseline value along with an increase in absolute value of 2 ng/mL or more. PSA progression (without evidence of progression on scans) will not be criteria for discontinuation of study therapy.
- PSA Response Duration: The PSA response duration commences on the date of the first 50% decline in PSA. The response duration ends when the PSA value increases by 25% above the nadir, provided that the increase in the absolute-value PSA level is at least 5 ng/mL or back to baseline, whichever is lower
- Progressive disease by PSA is defined by PSA progression, noted above.

- Time to PSA Progression: The start of the time to PSA progression is the day treatment is initiated. The end date is the date of the first PSA rise over the determined PSA PD value.

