## 2.3 Secondary Objectives and Endpoints

Secondary Objective	Endpoints	Time Frame
1. To determine safety of the combination of apalutamide and cetrorelimab	
 
Proportion of participants with treatment-related AEs, as graded by National Cancer Institute Common Terminology Criteria for Adverse Events (NCI CTCAE version 5.0)
 
	From initiation of study treatment until treatment discontinuation.
2. To determine the median radiographic progression-free survival by PCWG3 criteria	
 
Median progression free survival by PCWG3 criteria.
 
	From initiation of study treatment until radiographic progression by PCWG3 criteria or death, whichever occurs first.
3. To determine the PSA50 and PSA90 response proportion.	
 
<math>\geq 50\%</math> and <math>\geq 90\%</math> decline from baseline in PSA, respectively, confirmed by repeat measurement <math>\geq 4</math> weeks after first time point*
 
	From initiation of study treatment until maximal decline in serum PSA during study treatment.
4. To determine the median PSA progression-free survival.	
 
Median PSA progression-free survival by PCWG3 criteria.
 
	From initiation of study treatment until PSA progression by PCWG3 criteria or death, whichever occurs first.
5. To determine the median overall survival.	
 
Median overall survival from date of start of protocol treatment until death from any cause.
 
	From initiation of study treatment until death from any cause. (3 years)
6. To determine the objective response rate by RECIST 1.1 criteria	
 
Objective response rate by RECIST 1.1 criteria.
 
Median duration of response
 
	From initiation of study treatment until maximal percent decline from baseline in SLD of target lesions.

\* To be considered evaluable for this endpoint, patients must have baseline PSA level  $> 2$  ng/mL.

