### **3.5 Criteria for Treatment Discontinuation**

In the absence of treatment delays due to AEs, treatment (both study drugs) may continue until first occurrence of one or more of the following:

- Radiographic PD by PCWG3/RECIST 1.1 criteria. If patients are clinically stable in the judgment of treating investigator, continuation of protocol therapy is allowed until progression is confirmed by repeat tumor assessment performed  $\geq 4$  weeks following first scan demonstrating progression.
- Unequivocal clinical progression
- Inter-current illness that prevents further administration of treatment;
- Unacceptable AE(s);
- Participant decides to withdraw from the study;
- Significant participant non-compliance with protocol;
- Receipt of non-protocol therapy
- General or specific changes in the participant's condition render the participant unacceptable for further treatment in the judgment of the investigator
- Study closure
- Completion of 2 years of protocol therapy.

Patients with PSA-only progression in the absence of radiographic or unequivocal progression should remain on study treatment per PCWG3 guidelines.

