### 8.3.3 Secondary Analysis (or Analysis of Secondary Endpoints)

Secondary Objective 1 Analysis: AEs will be recorded and severity-graded using CTCAE version 5.0. Clinically significant laboratory, physical exam, scan, and ECG abnormalities will be captured as AEs. The frequency and severity of AEs will be descriptively reported on a per-patient analysis.

Secondary Objective 2 Analysis: The median radiographic progression-free survival determined by PCWG3 criteria

Secondary Objective 3 Analysis: PSA50 and PSA90 response are defined as above, a  $\geq 50\%$  and  $> 90\%$  decline from baseline in serum PSA, respectively, confirmed by repeat measurement  $\geq 4$  weeks later. The PSA50 and PSA 90 response proportions will be reported along with 95% confidence interval for each study cohort, for the subset of PSA-evaluable patients (serum PSA  $\geq 2$  ng/mL at baseline).

Secondary Objective 4 Analysis: Median progression-free survival will be determined for each cohort as from the date of first dose of protocol-defined therapy, using Kaplan-Meier product limit method. Progression is defined as per Section 7.1.4. The first scan time point demonstrating radiographic progression requires confirmatory scans performed  $\geq 4$  weeks after first scan time point to confirm progression. Patients who discontinue treatment for reasons other than those listed above (e.g. AE, patient withdrawal) will be censored by the date of last treatment.

Secondary Objective 5 Analysis: The median overall survival along with 95% confidence interval will be determined from the date of first dose of protocol-defined therapy until death from any cause, using the Kaplan-Meier product limit method. Patients will be followed for long-term survival as outlined in the Study Procedures. Patients who withdraw from study will be censored for analysis of overall survival using the date of study withdrawal.

Secondary Objective 6 Analysis: The objective response rate and median duration of response will be reported along with 95% confidence interval, for the subset of patients with measurable soft tissue disease by RECIST 1.1 criteria.

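### PSA progression is written as a single unconfirmed rise over the running nadir, which biases PSA-PFS towards early events when PSA is flat, slowly rising or responding

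*Combined protocol and SAP*

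**What the plan says.** Section 7.1.4 (Evaluation of Post-treatment PSA changes) sets the rule: "PSA progression occurs when the PSA has increased 25% or greater above nadir and an absolute increase of 2 ng/mL or more" from that nadir. For a patient whose PSA never falls, "Where no decline is observed, PSA progression similarly occurs when a 25% increase from baseline value" is seen together with the same 2 ng/mL margin. For time to PSA progression, "The end date is the date of the first PSA rise over the determined PSA PD value". No second value and no minimum time on treatment is required.

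The same section requires a decline to be "confirmed by a second measurement at least 3 weeks later". For bone disease, 7.1.4 asks for a confirmatory scan when new lesions appear at the first reassessment, and dates the event at the first scan.

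The endpoint in section 2.3 is "Median PSA progression-free survival by PCWG3 criteria", and 7.1.4 adds that "Prostate Cancer Working Group 3 (PCWG3) Criteria will be reported". The entry for secondary objective 4 in section 8.3.3 says "Progression is defined as per Section 7.1.4"; the only confirmation it mentions is of scans.

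Serum PSA is scheduled on Day 1 of every 28-day cycle and at End of Treatment, and not afterwards (sections 5.1, 6.1, 6.3). Section 3.5 says "Patients with PSA-only progression in the absence of radiographic or unequivocal progression should remain on study treatment".

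**The concern.** A rise is the only one of these PSA and imaging changes for which neither 7.1.4 nor 8.3.3 asks for a second look in any situation, yet it defines a named secondary endpoint. The reference value is the minimum of all earlier measurements, so it tends to lie below the patient's true level, and increasingly so as values accumulate. The 25% margin is therefore narrower than it looks, and the error runs in one direction, towards early events.

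A patient with no decline can be an event at Cycle 2 Day 1. Because PSA-only progressors stay on treatment, the same patient could later be a confirmed PSA50 responder. That makes PSA-PFS hard to read beside the primary endpoint. The value that would settle the matter is normally collected four weeks later anyway.

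**Working it through.** The plan gives no figure for PSA-PFS, so there is none to reproduce.

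**Inputs from the documents.** Event: value at least 1.25 × running nadir and at least nadir + 2 ng/mL, with the C1D1 value as baseline. PSA every 28 days. The two margins are equal at a nadir of 2 / 0.25 = 8 ng/mL. Above 8 the 25% governs; below it the 2 ng/mL does (a 40% rise at 5 ng/mL, 67% at 3 ng/mL).

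**Assumptions, not in the documents.** Log-normal within-patient variation with CV 5, 10, 15 or 20%, independent between visits. No deaths or dropout.

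**First post-baseline value, PSA truly flat, 25% margin governing.** With σ² = ln(1 + CV²), the log ratio of two values is N(0, 2σ²), so

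P(event) = 1 − Φ(ln 1.25 / (√2 σ)).

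At CV 10%: σ = 0.0998, √2 σ = 0.1411, 0.2231 / 0.1411 = 1.58, P = 5.7%.

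**Six cycles, PSA truly flat at 10, 20 or 50 ng/mL.** Simulated with 100,000 patients per cell and six post-baseline values. Confirmed means that the next value also meets the same threshold, the event is dated at the first value, and a seventh value may confirm a rise at the sixth.

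| CV | First value alone (formula) | Six cycles, single value | Six cycles, confirmed |
|---|---|---|---|
| 5% | 0.1% | 1.5% | 0.1% |
| 10% | 5.7% | 51% | 17% |
| 15% | 14.5% | 82% | 45% |
| 20% | 21.3% | 92% | 62% |

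The confirmed figure at CV 20% runs from 61% at 10 ng/mL to about 63.5% at 20 and 50 ng/mL. Over 12 cycles at CV 10% the pair is 84% vs 40%.

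**Low flat PSA, six cycles, single value vs confirmed.** At 5 ng/mL: 4% vs 0.1% (CV 10%) and 32 to 33% vs 5% (CV 15%). At 3 ng/mL, single value: 0% (CV 10%) and 2% (CV 15%).

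**Steadily rising PSA from 20 ng/mL.** Median event in 28-day cycles, 50,000 patients per cell, for CV 5/10/15/20%:

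| Doubling time | Noise-free | Single value | Confirmed |
|---|---|---|---|
| 2 months | 1 | 1/1/1/1 | 1/1/1/1 |
| 3 months | 2 | 2/2/2/2 | 2/2/2/2 |
| 4 months | 2 | 2/2/2/2 | 2/2/2/2 |
| 6 months | 3 | 3/2/2/2 | 3/3/3/2 |
| 12 months | 5 | 4/3/3/2 | 5/4/4/3 |

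From 5 ng/mL, a 4-month doubling time gives 2 vs 3 cycles at CV 15 to 20%. A 12-month doubling time gives 7/5/4/3 vs 7/7/6/5 (noise-free 7). If a month is counted as four weeks, the 3-month row from 20 ng/mL becomes 1 vs 2 at CV 15 to 20%, because growth per cycle then sits almost exactly on the 25% margin.

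**Is the confirming value available?** Day 1 visits carry a window of ±3 days, so consecutive ones are at least 28 − 3 − 3 = 22 days apart, which meets a 3-week interval.

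**The case against.** *PCWG3 is cited, so confirmation is implied.* A reader might infer this, or infer the reverse, that the plan departs from PCWG3. Its text is not in the documents, so neither can be shown. What can be shown is that 7.1.4 writes its own operative rule and ends the clock at the first rise. If confirmation was intended, the written rule misstates it.

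*The flat-PSA scenario is not this population.* This largely stands. Patients must be progressing at entry (3.3.1), and section 1.2 describes aggressive disease with a median of 3.0 months to progression on platinum. Where PSA climbs steadily and fast, the reported median moves little or not at all. Section 1.2 also links low PSA to this disease, and 3.3.1 admits patients with measurable disease whatever their PSA; for them the 2 ng/mL margin protects well at CV 10% or less. It would therefore be wrong to read 51% to 92% as the error rate expected in this trial.

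*Confirmation is neither free nor a cure.* This also stands. One confirming value leaves 17% false events at CV 10% and about half or more at CV 15 to 20%, because the nadir itself stays noisy. No PSA is scheduled after End of Treatment, so some last rises cannot be confirmed. Dropping all of those unless death follows would remove events from patients stopping for radiographic or clinical progression, and would bias PSA-PFS upwards.

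**Conclusion.** The point holds as a flaw in the written definition of one descriptive secondary endpoint. The single-value rule biases PSA-PFS towards earlier events in patients whose PSA is flat, slowly rising or responding. The false-event rate for flat PSA of 10 ng/mL or more ranges from 1.5% to 92% within six cycles across CV 5 to 20%, so the size cannot be fixed from the documents. In the rising-PSA settings tried, the gap between the single-value and confirmed medians was 0 to 1 cycle for doubling times of 2 to 4 months (none from 20 ng/mL) and 0 to 2 cycles for slower rises.

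A reader might infer that the trial's main conclusion or patient care is affected. The documents do not support that. PSA progression does not enter the composite response or the Simon rule (8.1.1, 8.3.2), is not progressive disease on its own (7.1.4), and does not stop treatment (3.5). The change is worth making because the direction of the bias is known and the data needed are already scheduled.

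**What to change.** Add to 7.1.4, and refer to it under secondary objective 4 in 8.3.3:

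> For the PSA-PFS analysis, PSA progression (from nadir, or from baseline where PSA never fell) must be confirmed by the next PSA, at least 3 weeks later, still meeting the same threshold, and is dated at the first of the two values. A rise at the last available PSA that cannot be confirmed counts as an event if the patient stopped treatment for radiographic or clinical progression or died; otherwise the patient is censored at that PSA. The single-value definition is reported as a sensitivity analysis.

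The general censoring sentence in 8.3.3, which uses the date of last treatment for patients who stop for other reasons, should be aligned with this. If the sponsor holds that PCWG3 already governs, the rule relied on should still be written out.

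Cost: a few sentences and one extra analysis, with no additional blood draws and no change to treatment. Downside: noise-driven events are reduced but not eliminated, and a few final rises will stay unconfirmed.
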